12.1 Treatment Emergent Adverse Events

Treatment-emergent adverse events (TEAEs) are defined as all AEs that begin on or after the date of the first administration of study drug. Related AEs are those reported as possibly related to SQL70 biopolymer, related to SPQ33 protodrug, and related to SQ3370 (both SQL70 and SQP33). The verbatim terms of the TEAEs will be coded to preferred terms (PT) and system organ classes (SOC) per the Medical Dictionary for Regulatory Activities (MedDRA®) Version 24.1.

All reported AEs (including non-TEAEs) will be listed, documenting all information collected on the eCRF including verbatim term, MedDRA preferred term, MedDRA system organ class, start date, stop date, severity and relationship to SQ3370 treatment, relationship to SQL70 biopolymer, relationship to SQP33 protodrug, action taken, and outcome.

The TEAEs will be graded by the Investigator in terms of:

- Severity graded 1-5 according to CTCAE v5.0:
 - 1=Mild, 2=Moderate, 3=Severe, 4= Life Threatening, 5=Fatal.
- Relation to SQ3370:
 - ‘Related’ includes events where the causality was reported as related to SQL70 biopolymer, related to SPQ33 protodrug, related to SQ3370 treatment (both SQL70 and SQP33), or where the relationship was not reported on the eCRF.
 - ‘Not Related’ includes events where the study drug causality was reported ‘Not Related’ on the eCRF.

All TEAE summary tables will be presented with the number and percentages of subjects in the Safety population. Incidence rates of treatment-emergent adverse events (TEAEs) will be summarized within each dose level at the Medical Dictionary for Regulatory Activities (MedDRA) primary system organ class levels and preferred term. Subjects may be counted under multiple system organ class (SOC) and preferred terms (PT), but for each SOC and PT category, subjects are only counted once. If a subject has the same AE on multiple

occasions, the highest severity grade (fatal > life threatening > severe > moderate > mild) or drug relationship (related > not related) recorded for the event will be summarized.

This list includes:

- All TEAEs
- All TEAEs graded severity
- All Related TEAEs to SQ3370 treatment
- All Related TEAEs to SQ3370 treatment graded by severity
- All Related TEAEs to SQL70 biopolymer
- All Related TEAEs to SQL70 biopolymer graded by severity
- All Related TEAEs to SQP33 protodrug
- All Related TEAEs to SQP33 protodrug graded by severity
- Serious TEAEs
- Adverse Event of Special Interest (AESI)
- Dose Limiting Toxicity (DLT)
- TEAEs leading to discontinuation from study
- TEAEs resulting in death.

Separate subject listings will be provided for all SAEs, AEs leading to study discontinuation, DLTs, AESIs, and deaths.

12.2 Serious Adverse Events

Incidence rates of serious TEAEs will be summarized within each dose level at the Medical Dictionary for Regulatory Activities (MedDRA) primary system organ class levels and preferred term A listing of subjects who reported a serious adverse event will be presented. The data will be obtained from the AE dataset where 'Is this adverse event serious? is checked 'Yes'.

12.3 Adverse Events Leading to Discontinuation from Study

Incidence rates of TEAEs leading to discontinuation from study will be summarized within each dose level at the Medical Dictionary for Regulatory Activities (MedDRA) primary system organ class levels and preferred term. A listing of subjects and the adverse events which led to study discontinuation from the study will be included. The specific AE will be identified from the AE dataset where 'Discontinued Study' is checked or has data within in.

12.4 Deaths Due to Adverse Event

Incidence rates of TEAEs leading to death will be summarized within each dose level at the MedDRA primary system organ class levels and preferred term. A listing of subjects who

died on study will be included. The specific AE leading to death will be identified from the AE dataset where 'Did the adverse event result in death?' is checked 'Yes'. Other possibilities are Outcome=Fatal and/or CTCAE Grade=5.

12.5 Adverse Event of Special Interest (AESI)

Incidence rates of TEAEs of special interest will be summarized within each dose level at the MedDRA primary system organ class levels and preferred term. All AESIs will be listed by dose cohort and subject.

AESIs will be defined as DLTs and the preferred terms of potential myocardial toxicity, pregnancy, COVID-19 infections, and AEs due to overdose. The specific AESI will be identified from the AE dataset where AESI is checked.

12.6 Dose Limiting Toxicity (DLT)

For dose escalation the protocol defined DLT for a 21-day cycle (Cycle 1) using the protocol dose escalation DLT definitions and criteria following review by the Safety Review Committee (SRC), incidence rates of dose limiting toxicities will be summarized within each dose level at the MedDRA primary system organ class levels and preferred term. All DLTs will be listed by dose cohort and subject. The specific DLT will be identified from the AE dataset where AEDLT is checked.

12.7 Clinical Laboratory Tests

Safety laboratory assessments will be conducted on as specified in Schedule of Assessments (Section 18).

All laboratory tests, values, units, normal ranges, flags collected in the clinical database (i.e., results that are outside the normal ranges will be flagged with "L" (below normal range) or "H" (above normal range)) will be included in the-subject listings for further medical review.

For laboratory analysis, baseline will be defined as either the screening visit or the Cycle 1 Day 1 visit; whichever is the closest visit prior to the administration of study treatment.

12.7.1 CTCAE Grading

For the hematology laboratory tests of interest where CTCAE [version 5.0] severity criteria are specified, CTCAE severity grades will be assigned. These laboratory tests include:

| Panel | Test | CTCAE grade directions |
|--------------|-------------|-------------------------------|
| Hematology | ANC | Decrease |
| | Hemoglobin | Decrease / Increase |

| | | |
|--|------------------------------|----------|
| | Platelet Count | Decrease |
| | White Blood Cell (WBC) count | Decrease |
| | Lymphocyte Count | Decrease |

Analyses will be performed using “shift tables” of CTCAE toxicity grades relative to the baseline (pre-treatment) toxicity grade. The number and proportion of subjects with directional shifts of the “worst” CTCAE toxicity grade post-baseline and CTCAE toxicity grade of the last post-baseline visit relative to the baseline (pre-treatment) toxicity grade will be summarized for the selected hematology and chemistry parameters.

The CTCAE toxicity grading algorithms for the appropriate laboratory analytes are detailed in Section 19.

12.7.2 Hematology

Hematology laboratory tests are planned to include Hemoglobin, Hematocrit, MCV, Platelets, Absolute White Blood Count, Absolute Neutrophil Count, Absolute Lymphocyte Count, Absolute Monocyte Count, Absolute Eosinophils Count, Absolute Basophils Count, % Neutrophils, % Lymphocyte, % Monocytes, % Eosinophils, and % Basophils.

Due to the large number of laboratory visits, the data will be summarized by these post-baseline timepoint descriptors: First post-baseline, Last post-baseline value, Minimum post-baseline value, Maximum post-baseline value, and Average post-baseline value.

These hematology laboratory test results are measured on a continuous scale and the observed values as well as changes from baseline values will be summarized for each dose cohort using n, mean, standard deviation, median, minimum and maximum values.

12.7.3 Chemistry

Chemistry laboratory tests are planned to include Sodium, Potassium, Glucose, Calcium (Total), Creatinine, Protein (Total), Albumin, Bilirubin (Total), Bilirubin (Direct), Alkaline Phosphatase (ALP), Aspartate Aminotransferase (AST), Alanine Aminotransferase (ALT), Lipase, Amylase.

Due to the large number of laboratory visits, the data will be summarized by these post-baseline timepoint descriptors: First post-baseline, Last post-baseline value, Minimum post-baseline value, Maximum post-baseline value, and Average post-baseline value.

These chemistry laboratory test results are measured on a continuous scale and the observed values as well as changes from baseline values will be summarized for each dose cohort using n, mean, standard deviation, median, minimum and maximum values.

12.7.4 Coagulation

Coagulation laboratory tests are planned to include Prothrombin Time (PT), Activated Partial Thromboplastin Time (aPTT), Thrombin Time (TT) and INR.

Due to the large number of laboratory visits, the data will be summarized by these post-baseline timepoint descriptors: First post-baseline, Last post-baseline value, Minimum post-baseline value, Maximum post-baseline value, and Average post-baseline value.

These coagulation laboratory test results are measured on a continuous scale and the observed values as well as changes from baseline values will be summarized for each dose cohort using n, mean, standard deviation, median, minimum and maximum values.

12.7.5 Urinalysis

All Urinalysis test results (Protein, Blood, Specific Gravity, Glucose) will be presented in the subject listings.

12.8 Vital Signs and Weight

The vital sign tests to be collected include:

- Blood pressure (systolic and diastolic [mmHg])
- Heart rate (beats per minute [bpm])
- Respiratory rate (bpm)
- Temperature (c)
- Weight (lbs) once per cycle
- Height (in) at screening only.

See Schedule of Assessments (Section 18) for specific vital sign data collection timepoints.

Vital sign assessments measured on a quantitative scale will be summarized in a descriptive manner by calculating the n, mean, standard deviation, median, and range at the baseline timepoint (defined as either the screening visit or the Cycle 1 Day 1 visit; whichever is the closest visit prior to the administration of study treatment) and subsequent post-baseline timepoint, and by dose cohort. Mean change from baseline will also be presented in the same manner.

Due to the large number of vital sign visits, the data will be summarized by these post-baseline timepoint descriptors:

- First post-baseline, Last post-baseline value, Minimum post-baseline value, Maximum post-baseline value, and Average post-baseline value.
- Height will only be summarized at baseline.

All vital sign tests will be included in subject listings for further medical review.

12.9 12-Lead Electrocardiogram (ECG)

The 12-Lead ECG assessments include:

- Heart Rate
- QT interval
- PR interval
- QRS interval
- QTcF interval

See Schedule of Assessments (Section 18) for specific ECG data collection timepoints. In summary they include:

- Screening.
- On Day 1 of each cycle ECGs will be performed both pre and post SQP33 protodrug infusion.
- On Days 2-5 of Cycle 1 ECGs will be performed post SQP33 protodrug infusion only.

Quantitative Analysis:

ECG assessments measured on a quantitative scale will be summarized in a descriptive manner by calculating the n, mean, standard deviation, median, and range at the baseline timepoint (defined as either the screening visit or the Cycle 1 Day 1 visit; whichever is the closest visit prior to the administration of study treatment) and subsequent post-baseline timepoint, and by dose cohort. Mean change from baseline will also be presented in the same manner.

Categorical Analysis:

Additionally, QTcF results will also be categorized according to their values into the categories as defined in ICH E14:

- ≤ 450 ms
- > 450 ms to ≤ 480 ms
- > 480 ms to ≤ 500 ms
- > 500 ms

and categorized according to their change from baseline into the categories:

- ≤ 30 ms,
- > 30 ms to ≤ 60 ms
- > 60 ms

The categories described above will be summarized in frequency tables using number of subjects (n) and percentages at each post-dose timepoint for each dose cohort

A separate analysis of the overall ECG interpretation (categorical: Normal, Abnormal Not Clinically Significant, and Abnormal Clinically Significant) will be performed using “shift tables” relative to the baseline (screening) interpretation. The number and proportion of subjects with directional shifts of ECG interpretation categories post-baseline relative to the baseline (screening) will be summarized.

All ECG results will be included in subject listings for further medical review. Of specific interest would be the interpretation of Abnormal, Clinically Significant ECG panel.

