Safety	Symptom-Directed PE	X ^B			X	
	Vital Signs	X	X	X	X	
	ECHO or MUGA	X ^C			X ^I	
	TriPLICATE 12-Lead ECG	X ^{B, D}			X	
	ECOG	X ^B			X	
	AE Review	X	X	X	X	
	Conmed Review	X	X	X	X	
Labs	Hematology & Chemistry	X ^B		X	X ^B	
	Coagulation & Urinalysis	X ^B			X ^B	
	Pregnancy Test	X ^B			X ^B	
	Optional Tumor Biopsy	X ^H				
Tumor Evaluation	CT / MRI & RECIST	Every 6 weeks ^E			X ^K	X ^M
IP ^F	Administer SQL70 Biopolymer	X				
	Administer SQP33 Protodrug	X ^G	X	X		
Survival	Vital Status ^L					X

Notes:

A - Day 1-5 is typically Monday through Friday, however if the site can accommodate protocol procedures on the weekends Day 1 may start on any day of the week.

B - May be performed up to 3 days before the visit.

C - May be performed up to 7 days before the visit.

D - ECG to be performed pre and post dose.

E - May be performed up to 7 days prior to the projected every 6 weeks from C1D1 date.

F - IP administration is the last procedure for each visit (aside from post-dose vitals and ECG).

G - SQP33 protodrug infusion occurs within 2 hrs ± 30 mins after receiving SQL70 biopolymer injection.

H - Optional biopsy per investigator discretion; can be performed up to 4 days prior to Day 1.

I - ECHO or MUGA not required at the Safety Follow-Up visit if performed in the previous 14 days.

K - CT / MRI & RECIST not required at the Safety Follow-Up visit if performed in the previous 6 weeks.

L - for up to 2 years after treatment end; collected during routine clinic visits, telephone or e-mail with the subjects/caregivers or referring physician offices.

M - Until disease progression per RECIST; May be performed up to 14 days before the visit.

Reminder: Investigator can perform unscheduled labs, ECGs and physical exams as needed / clinically indicated.

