9.5.3 Other Situations

For subjects who are withdrawn from the study prior to study completion, all data compiled up to the point of discontinuation will be used for analysis. All withdrawals will be included in all analyses up to the time of withdrawal.

Extra measurements (such as unscheduled or repeat assessments) will not be included in summary tables but will be included in subject listings. They will be used in summary tables which are not 'time specific', for example, summaries of first, last, minimum, maximum, and average post dose values.

The original data will always be presented in the listings.

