- > 60 ms

The categories described above will be summarized in frequency tables using number of patients (n) and percentages at each post-dose timepoint for each expansion group.

A separate analysis of the overall ECG interpretation (categorical: Normal, Abnormal Not Clinically Significant, and Abnormal Clinically Significant) will be performed using “shift tables” relative to the baseline (screening) interpretation. The number and proportion of patients with directional shifts of ECG interpretation categories post-baseline relative to the baseline (screening) will be summarized.

All ECG results will be included in patient listings for further medical review. Of specific interest would be the interpretation of Abnormal, Clinically Significant ECG panel.

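### No summary specified in either SAP counts the patients whose QTcF ever exceeded 500 ms or rose by more than 60 ms, because the categories are tabulated only by scheduled timepoint

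*SAP*

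**What the plan says.** **QTcF categories.** Section 12.9 of the Phase 1 SAP states: "Additionally, QTcF results will also be categorized according to their values into the categories as defined in ICH E14". The four bands are up to 450, above 450 to 480, above 480 to 500, and above 500 ms. QTcF is also "categorized according to their change from baseline into the categories" of up to 30, above 30 to 60, and above 60 ms. Both sets are "summarized in frequency tables using number of subjects (n) and percentages at each post-dose timepoint for each dose cohort". Section 12.9 of the Phase 2a SAP has the same rule, with "percentages at each post-dose timepoint for each expansion group".

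**Unscheduled ECGs.** Protocol Appendix G says: "Investigator can perform unscheduled labs, ECGs and physical exams as needed / clinically indicated". The Phase 1 SAP (sections 8.4 and 9.5.3) says: "Extra measurements (such as unscheduled or repeat assessments) will not be included in summary tables but will be included in subject listings". Both sections make an exception for tables not tied to a timepoint, such as minimum, maximum or last value. Section 9 also excludes unscheduled visits from summary tables. The Phase 2a SAP repeats these rules under the same section numbers.

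**Baseline.** For the ECG intervals, section 12.9 takes screening or Cycle 1 Day 1, "whichever is the closest visit prior to the administration of study treatment". For the shift in overall ECG interpretation, the same section works "relative to the baseline (screening) interpretation".

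**The concern.** ECG change is part of the primary safety endpoint in both phases (Protocol 2.1.2.1 and 2.2.2.1), and Protocol 7.5.4 treats ECG changes as a possible sign of anthracycline cardiomyopathy. With an outlier threshold, the natural question is how many patients at a dose level ever crossed it. A table built visit by visit does not answer that, because the same patient may be counted at several visits. Nor does it capture ECGs taken between visits for a clinical reason.

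The SAPs handle most comparable data differently. Hematology, chemistry, coagulation and vital signs get minimum and maximum post-baseline summaries. Hematology toxicity grades and ECOG get a worst post-baseline value. ECG intervals get neither.

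The baseline difference matters less but is real. A change in the ECG reading between screening and the Cycle 1 Day 1 pre-dose ECG would be displayed as a shift on treatment.

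**Working it through.** There is no stated figure to reproduce. The check has four parts.

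**1. Is a per-patient QTcF count specified elsewhere?** Section 12.9 of the Phase 1 SAP contains three summaries:
- Interval values and changes are summarised at baseline and by post-baseline timepoint. The range is given at each timepoint, but no maximum post-baseline descriptor is defined.
- QTcF categories are counted at each post-dose timepoint.
- The overall interpretation (normal, abnormal not clinically significant, abnormal clinically significant) is shown as a shift. This does not use the QTcF thresholds.

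None counts patients by their highest QTcF. The exception that admits unscheduled data needs a table not tied to a timepoint, and no such QTcF table is defined. All ECG results, scheduled or not, go to listings.

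**2. How many scheduled timepoints?** From Protocol Appendix G, for a Phase 1 patient completing 12 cycles:
- Cycle 1: post-infusion on Days 1 to 5, plus Day 17: 5 + 1 = 6
- Cycles 2 to 12: one post-infusion ECG on each Day 1: 11 × 1 = 11
- Safety follow-up: 1
- Total: 6 + 11 + 1 = 18

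This counts Day 17 and safety follow-up as post-dose timepoints. Adding the 11 pre-infusion Day 1 ECGs of Cycles 2 to 12 gives 18 + 11 = 29.

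**3. What do by-visit counts determine?** Let c_t be the number of patients above the threshold at timepoint t, in a cohort of n. The number ever above it, on scheduled ECGs, satisfies

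max(c_t) ≤ ever above ≤ min(n, Σ c_t).

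The documents give no QTcF rates, so these are illustrations:
- n = 6, one patient at each of two timepoints: 1/6 (16.7%) to 2/6 (33.3%)
- n = 6, one patient at each of four timepoints: 1/6 (16.7%) to 4/6 (66.7%)
- n = 6, one patient at each of the six Cycle 1 timepoints: 1/6 (16.7%) to 6/6 (100%)
- n = 1 (accelerated titration): no ambiguity

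If every cell is zero, or only one timepoint has a non-zero cell, the scheduled count is determined. A patient whose only excursion was on an unscheduled ECG adds 0 to every cell in all cases.

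**4. Baselines side by side.** Section 8.6 takes the latest measurement at screening or before first dose. Section 10 takes the last value before the first study treatment. The interval analysis in 12.9 takes the closest pre-treatment visit. The interpretation shift alone names screening. Under Protocol 6.9.1 the screening ECG is also the only one not taken in triplicate. The shift text does not say which post-baseline ECG is compared.

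**The case against.** A reader might infer that the outlier count is lost or cannot be obtained. The documents do not support that. Section 12.9 places all ECG results in listings, which include unscheduled data. With 39 patients treated in Phase 1 (Protocol 1.4) and cohorts of 1 or 3 to 6, a hand count is feasible. Any scheduled value above 500 ms also shows as the top of that visit's range.

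A reader might also infer that a QTcF above 500 ms on an ECG taken for symptoms would appear in no table. That goes too far. Protocol 7.1.1 makes a new clinically significant or symptomatic diagnostic abnormality an adverse event, and the adverse-event tables count each patient once per preferred term at the highest grade. New arrhythmia or heart block falls under potential myocardial toxicity, an event of special interest with its own summary. What is missing is the numeric QTcF category. Whether an excursion becomes an adverse event rests on symptoms or investigator judgement, not on the SAP's thresholds, so this route does not replace the count.

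Nor is QTcF singled out: LVEF (section 12.11) is also summarised only by timepoint. And nothing in the documents shows that unscheduled ECGs are the ones most likely to carry an excursion.

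Finally, the SAPs say that table shells form part of them, and the shells are not in the text available. A maximum QTcF row there cannot be excluded, but the text specifies none. The analysis is descriptive, and no document promises an any-time outlier proportion. That limits the weight of the point without removing it.

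**Conclusion.** The point stands as a gap in the planned summaries, in both SAPs. The categories are defined, but the specified tables do not generally yield the number of patients ever above 500 ms or ever more than 60 ms above baseline, and unscheduled ECGs do not enter them. The size depends on data not given: there is no ambiguity in single-patient cohorts or when at most one timepoint has an excursion, and a span from 17% to 67% in the four-visit illustration for a cohort of 6. The timepoint figure is 18, for a patient completing all 12 cycles; 29 applies only if pre-infusion ECGs are counted. The separate baseline inconsistency is confined to the interpretation shift table.

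This rests on the SAP text without its table shells. It is worth correcting because the data concern a primary-endpoint component and are already collected. It does not mean that QTcF excursions would go unrecorded.

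**What to change.** In section 12.9 of the Phase 2a SAP, add for each group the number and percentage of patients by maximum post-baseline QTcF category and by maximum increase from baseline. Cover all scheduled and unscheduled ECGs, and use the mean of each triplicate where one was taken. Keep the by-visit tables.

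For the interpretation shift, use the last ECG before first study treatment as baseline, consistent with sections 8.6 and 10, and take the shift to the worst post-baseline interpretation.

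The Phase 2a SAP is marked version 0.1 with an incomplete date, so it can be edited directly. It describes the Phase 1 SAP as already executed, so there the same tables can come through an SAP revision (Phase 1 SAP 8.4) or as an additional analysis described in the study report (Phase 1 SAP section 1).

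No new data are needed: Protocol 6.20 already requires unscheduled-visit data in the eCRF. The cost is a small amount of extra table programming.
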